D. 3. 4. Rationale for Cognitive Testing A three-year study of 3,217 elderly residents of Cache County, Utah, initially found that the use of some antihypertensive medications at baseline was associated with lower incidence of AD. More recently, ACE-I have been shown to influence cognitive task performance in clinical trials specifically targeting AD related memory problems. Of note, the current proposed study will incorporate the same cognitive outcome measure (the MMSE) that has been shown to be sensitive to ACE-I treatment. Two clinical trials, Syst-Eur and PROGRESS both reported improved cognitive test scores in participants with mild to moderate AD (controlled for vascular dementia) as a result of treatment with ACE-I.

Furthermore, Sink et al. examined the influence of ACE-I that do and do not cross the blood brain barrier (BBB). The authors concluded that BBB crossing ACE-I participants in the BBB crossing group had a significantly lower incidence of developing AD as well as significantly reduced MMSE decline in AD patients compared to CCB and ACE inhibitors. This factor is of particular relevance because the ACE-I in the current proposal, ramipril, is an ACE-I that crosses the BBB. These results were presented at the AGS 2007 Annual Scientific Meeting: Abstract P36. Presented May 5, 2007.

D. 4. Data Analysis and Statistical Considerations The study objective is to evaluate the effects of 4 months of ramipril therapy vs. placebo on mean changes in CSF A β , ACE and mean changes in measures of peripheral endothelial function. While we are not aware of any research examining the effect of ACE-Is on CSF A β , cognitive improvements due to ramipril have been reported in as few as 5 days [29]. In reference to reductions in plasma ACE, ramipril is one of the most potent ACE-Is available and has a trough-to-peak ratio around 50% [106, 107]. When ACE-Is are injected intracerebroventricularly, A β reduction can occur in as few as 2 hours. A sample size of 10 subjects per arm should have greater than 80% power to detect an 8% change in CSF A β , the primary outcome, and greater than 90% power to detect significant

change in endothelial variables. Based on the sample size estimates, 20 subjects will be recruited for the 4-month clinical trial.

Clinical outcome parameters will be described by means and standard deviations at each measurement time point. Regression models will be used to evaluate predictors of change in CSF variables and endothelial outcomes. Changes in clinical outcome parameters (baseline, month 4) will be analyzed using repeated-measures analysis of variance (ANOVA) to assess the effects of ramipril vs. placebo, using covariates as applicable (ANCOVA). All tests will be two-tailed tests using a significance level of 0.05.

All data for the SEAIRA trial has now been collected at the UW Madison. Data collected as a part of this study will be shared with [name], the prior PI of the SEAIRA study, now Assistant Professor at Emory University. While at Emory University, [name] plans to continue analyses on data collected during her time at the University of Wisconsin. We propose that this study now become a two-site study with [name] mentor and Co-I, [name] as the site PI for the University of Wisconsin. All physical data, data specimens including stored CSF and blood will remain at the UW. The study should however remain open so [name] may continue data analyses for this study. [name] will conduct the analyses at Emory with coded data. The UW ADRC research team will be the only institution with access to this code.

While SEAIRA is now complete, additional analyses on data from this trial need to be conducted. To accomplish this goal, data must be transferred to Emory University from the UW. Data will be sent electronically via email from the ADRC research team at UW Madison to [name] at Emory University. The transfer will be overseen by new UW PI of the project – [name]. All transmitted data will be coded. The code used to label data will be separate from the previously used SEAIRA trial ID number, so that [name] will not know or have access to the key linking identities with the data. Data to be transferred consists of neuropsychological testing data, ApoE4 genotype, abeta and ACE levels and activity in CSF, family history status, race, gender, age, self-reported income category, handedness, education level, drug randomization assignment, symptom reports during the trial, lab data including HDL, LDL, cholesterol levels, potassium, creatine, CSF cell count, smoking history, exercise history, medication and medical history information and data confirming study medication compliance.

Data will be transferred immediately upon IRB approval. A member of the UW ADRC research team will transfer the coded data via email to [name] at Emory. A data transfer will occur once IRB approval has been granted at both the UW and Emory University. This transfer will include an Excel and SPSS spreadsheet that was created by [name] and contains all participant data collected thus far and is detailed above. All data to be transferred to Emory University will be coded and UW Madison will retain the key linking subject identities with the code numbers. [name] will not have access to this key.

At Emory University, [name] will store the data on her personal work computer. This computer is password protected, and the data saved on it is saved to a secure server. [name] computer is locked in her office when she is not there.

The University of Wisconsin will serve as the lead site/coordinating center for the study as all physical data, data specimens including stored CSF and blood will remain at the University of Wisconsin; however further data analysis will be conducted at both the UW and Emory University. [name] will be responsible for receiving and analyzing data and developing and updating the study protocol as needed. The University of Wisconsin will communicate with and

disseminate information to [name] at Emory as needed to discuss anything related to the physical data, W-ADRC or IRB requirements; however Emory will be responsible for communicating to the University of Wisconsin regarding data analysis progress, protocol updates or other changes to the study. Any unanticipated events or new information about the study will be disseminated to the University of Wisconsin and Emory University immediately.

The UW HS IRB will remain the IRB of record; however Emory University will provide approval of their involvement with the study (data analysis by [name] only).

E. Human Subjects Research The University of Wisconsin has a humans subjects research Multiple Projects Assurance on file with the Office for Protection from Research Risks (M-1285). Furthermore, all key personnel have completed an educational program entitled “Human Subjects Protection Tutorial at the University of Wisconsin-Madison,” adapted from the NIH Computer Based Training on Protection of Human Subjects. (A copy of the UW Human Subjects Training Certification Letter is included in the application.) In addition, all key personnel have completed appropriate training for the Health Information Portability and Accountability Act (HIPAA). [name], now at Emory University, has completed both Human Subjects and HIPAA training required by Emory University. Emory IRB reviewed the current project and determined that no IRB Review will be required at Emory.

E. 1. Involvement of Human Subjects. Twenty middle-aged, asymptomatic adult children of persons with AD will be randomized for this 4 month RCT. Subjects will be between the ages of 40 to 70 years. Special classes of subjects such as children, pregnant women, prisoners, and institutionalized individuals will not be enrolled. Children are specifically excluded because the goal of the study is to evaluate the effects of antihypertensives in adult children of patients with AD. In order for young children to participate, one of their parents must have AD, meaning the parent would most likely be fairly young and have early-onset AD, which is clinically different from late-onset AD. **Young children** are not included in our study. **Pregnant women** are excluded because of regulations barring them from this type of research (*i.e.* the effects of ramipril are designated as pregnancy category ‘D’ by the Food and Drug Administration (FDA). This means that there have been studies in pregnant women that show the drug was associated with some risk for the fetus. Specifically, the use of ACE inhibitors during the second and third trimesters of pregnancy has been associated with fetal and neonatal injury including hypotension, neonatal skull hypoplasia, anuria, reversible or irreversible renal failure, and death. Current Wisconsin Registry for Alzheimer’s Prevention (WRAP) participants are also excluded because the neuropsychological test battery may interfere with the primary endpoints of the WRAP study. Other exclusion criteria for study participants are listed in Section D.1. and Table 1. Subjects will complete health-related questionnaires, have fasting blood tests, lumbar punctures, and cognitive testing according to the study protocol summarized in Figure 3. All data for this trial has been collected and no further data collection will take place. In addition to data being coded with unique identifiers not known to [name], data is also now coded so as to not show identifiers such as DOB and visit date. These dates are now coded to reflect birth and visit month and year, but not the specific date of either.

E. 2. Sources of Research Material. CSF will be collected from subjects in this study for testing related to CSF A β and ACE levels. Blood samples will also be collected to monitor medication side effects and laboratory safety values. These specimens will be obtained specifically for research purposes and to ensure the safety of participants.

E. 3. Recruitment and consent procedures. Detailed recruitment procedures are described in Section D.1. If registrants are interested in participating, a research staff will meet with them to review the inclusion and exclusion criteria, risk, benefits, and consent form with them. Subjects will be given opportunity to review the risks and benefits of participating in the study and have their questions answered. A copy of both of the consent forms will be given to each subject.

All data collection for this study is now complete and no further participants will be recruited or enrolled. The data is being used in a manner to which the participants previously provided written consent and the original PI of the study is the individual requesting the data for purposes of data analysis and publication.

E. 4. Potential risks.

E. 4. 1. Cognitive testing: This is well tolerated by patients. Participants could become tired or frustrated by the difficulty of the cognitive tasks. However, the cognitive testing will last only approximately 1.5 hours, which is a relatively short duration in comparison to similar IRB approved protocols.

E. 4. 2. Neuroimaging:

E. 4. 3. Lumbar punctures: The most common complication of lumbar puncture is post-dural puncture headache. The rate of headache occurrence can be reduced to as low as 1.7% with use of an atraumatic 21-gauge Sprotte spinal needle [108] with a very small gauge (25 gauge with introducer), and using a gentle extraction technique now widely used in AD research. Bacterial meningitis is a very rare complication of lumbar puncture, occurring in fewer than 0.2% in one series [109]. Uncal or tonsillar herniation is a very uncommon complication, occurring in <1% of very high-risk subjects with known primary or metastatic neoplasms who underwent a lumbar puncture [110]. Using a smaller (24-gauge) Sprotte needle in this trial, we anticipate a reduction in post-LP headache rates to 5% (from our current rate of 9.3%). Only one of our previous subjects required a blood patch for the headache. Serious post-LP complications such as adhesive arachnoiditis are extremely rare, with estimates close to 0.4-0.6 per 10,000 procedures [111]. Therefore, we do not anticipate such significant complications during the course of this study. [name] will perform a neurological and fundoscopic exam on each subject prior to lumbar puncture and those participants thought to have papilledema or gross neurologic deficits consistent with a central nervous system mass will not have a lumbar puncture performed. Each subject will be called the day following his or her lumbar puncture to ask about any side effects. All subjects will be given a telephone number to reach a physician 24-hours per day.

E. 4. 4. Social: The social risk is a breach of confidentiality regarding risk for development of AD. Subject names and research data will be handled with utmost confidentiality and discretion. Subjects will be assigned a unique identification number that can be traced only by the research coordinator and Principal Investigator. All subject information will be kept in locked drawers, file cabinets, or secure computer files, with access only allowed to research personnel.

E. 4. 5. Ethical, Psychological, Legal, Other. Although participants will be given information on their plasma lipoprotein subclassification at the conclusion of their participation, they will not be given information about their APOE4 status, CSF or plasma biomarkers. This will be clearly

stated in the informed consent process. Although APOE4 allele is associated with a higher risk of developing AD, not all people with APOE4 develop AD and not all AD patients are APOE4 allele carriers. Also, there are no clear standards in cognitively healthy adults for identifying higher risk individuals using CSF or plasma biomarkers. Furthermore, although these markers *may* predict who is at higher risk of developing AD, they are still in the research stages and do not have proven roles in clinical practice. In addition, since there are no established effective preventive therapies for AD, providing individuals with individual risk data may only add to their psychological burden and not provide them any benefit. If, during the course of the study, a new medication is approved by the FDA for AD prevention in high-risk individuals, then current policies will be revised to ensure good clinical care for study participants. Insurability of participants may be affected if there is any breach of confidentiality, which we do not anticipate.

E. 5. Protection of Subjects. As stated above, the physical, social, and psychological risks associated with this study are small. Subjects will not be allowed to participate if their physician does not feel that it would be safe or prudent for them to do so. Subjects will be monitored for 30 minutes after lumbar puncture and will be called the next day after the procedure to inquire about adverse effects. Confidentiality will be assured by assigning a unique subject number to each subject. All subject information will be kept in locked drawers, file cabinets, or secure computer files, with access only allowed to research personnel. Data from this study may be shared with researchers of an associated protocol involving exercise and Alzheimer's disease risk in the event that the subject consents to participate in the associated exercise protocol. All data and samples will be housed at UW Madison.

E. 6. Risks and expected benefits for subjects and society. As above, the risks associated with this study are small. Although individual participants may not derive clinically apparent cognitive benefits from ramipril during the course of the study, they may benefit from future research that builds on these data should ACE-I eventually be proven to have a role in AD prevention. Subjects will receive free fasting lipid profiles as part of this study. Subjects will receive honoraria to reimburse them for their time and effort.

The benefits to society may be considerable. Society, specifically individuals at risk for AD, will benefit by learning if the markers indicating risk for cognitive decline can be modified by ACE-I therapy. This knowledge could affect decisions regarding initiation of ACE-I therapy for prevention of AD. Since the completion of this study, the PI and others have conducted similar research showing the protective effects of RAS acting antihypertensives on multiple outcomes including hippocampal volume, cerebral blood flow, brain inflammatory markers, cognitive function and perhaps most importantly, reduced disease progression from MCI to AD over a 4 year period.

E. 7. Inclusion Report

E. 7. 1. Inclusion of Women. All participants will be invited through clinic visits, recruitment registry or individual flyers to participate in this study. Since approximately 70% of AD cases are women, we expect that percentage to be reflected in our study population and we will emphasize the importance of AD prevention research in the context of women's health to those invited to participate.

E. 7. 2. Pregnancy and Contraception: For women of child bearing potential, it is important to note that ACE inhibitors are labeled with a pregnancy ‘category D’ by the Food and Drug Administration (FDA). This means that there have been studies in pregnant women that show the drug was associated with some risk for the fetus during the 2nd and 3rd trimesters. Because of this, premenopausal females who have not had a hysterectomy must agree to use at least one form of contraception during the study, in addition to a male partner who correctly uses a condom or is sterile. The medically accepted methods of birth control to use while enrolled in the study are:

- Oral contraceptives (either combined or progesterone only)
- Intrauterine device (IUD)
- Transdermal contraceptive patch
- Injectable progesterone
- Implants of levonorgestrel
- Double barrier method: condom + cervical cap or diaphragm with spermicidal agent

<<http://www.fda.gov/CDER/drug/advisory/ACEI.htm>>

E. 7. 3. Inclusion of Minorities: Since enrollment in this study requires subjects to come to UW CTRC for testing, the registrant population is primarily from Dane County. According to the 2000 Census, Dane County’s total minority population between the ages of 45 to 70 years was 3% of the population (see Table 2). Based on this statistic, we will attempt to enroll 1-2 minorities.

Table 2. Dane County, Wisconsin, 2000 Census Data

	Number	%
Race/Ethnicity	Ages 45-64	Ages 45-64
White	85,244	93.7%
Black	2,187	2.4%
Hispanic	1,291	1.4%
Asian/Pacific Islander	1,522	1.7%
American Indian, Eskimo, or Aleut	217	0.2%
Other race	560	0.6%

E. 8. Data Safety and Monitoring

All participants will provide informed consent and the study will be overseen by a Data Safety and Monitoring Board (DSMB) consisting of a physician and statistician who are not directly involved in the study. [name] is a physician who has served on DSMBs and has worked with the PI and Co-Is on previous projects. Similarly, [name] MS, is a biostatistician who has also worked with the PI and Co-Is and has also been directly involved in clinical trials investigating the effects of statins on CSF A β and cognitive outcome variables. Additionally, [name] (Co-I) will serve on the DSMB and will be primary physician involved in this study. All side effects will be closely monitored. The most common side effects of ACE-I are mild cough, hyperkalemia or changes in kidney function. The most common side effect of lumbar puncture (LP) is headache, which is usually self-limited. At UW, the rate of headaches following LP is less than 5%. [name] will perform lumbar punctures for the proposed trial and has significant experience with this procedure, having performed over 260 lumbar punctures in the last five years with no complications. Participants will receive a phone call 24 hours after the LP to inquire about any post-procedure adverse effects. According to the Joint National Committee on Prevention (JNCP) VII guidelines, a dietary intervention for mild BP elevation for 4 months is

within the standard of clinical care [112]. All participants will receive wellness program information, which includes the DASH lifestyle intervention. Compliance will be measured via self report. Participants with contraindications to ACE-I therapy or LP will be excluded from participation. All subjects will be monitored for high blood pressure (systolic > 160 or diastolic > 100) and other possible side effects at each visit. At each visit, participants will be screened with blood pressure readings, blood tests, possible pregnancy tests and questionnaires to inquire about potential side effects. Participants with elevated potassium or creatinine will be advised to stop treatment and will have follow up labs until the abnormalities resolve. Should a participant's BP rise to unsafe levels (systolic > 160 or diastolic > 100) the participant will be advised to visit his/her primary care physician and the DSMB will be notified immediately. CSF collection will be completed according to guidelines put forth in the "NIA Biospecimens Best Practice Guidelines for the Alzheimer's Disease Centers." Once enrollment has ended, the DSMB will no longer meet; however will be available on an as-needed basis.

References

1. McKhann, G., et al., *Clinical diagnosis of Alzheimer's disease: report of the NINCDS-ADRDA Work Group under the auspices of Department of Health and Human Services Task Force on Alzheimer's Disease*. Neurology, 1984. **34**(7): p. 939-44.
2. Birns, J., et al., *The effects of blood pressure reduction on cognitive function: a review of effects based on pooled data from clinical trials*. J Hypertens, 2006. **24**(10): p. 1907-14.
3. Staessen, J.A., et al., *Randomised double-blind comparison of placebo and active treatment for older patients with isolated systolic hypertension. The Systolic Hypertension in Europe (Syst-Eur) Trial Investigators*. Lancet, 1997. **350**(9080): p. 757-64.
4. Eckman, E.A., et al., *Regulation of steady-state beta-amyloid levels in the brain by neprilysin and endothelin-converting enzyme but not angiotensin-converting enzyme*. J Biol Chem, 2006. **281**(41): p. 30471-8.
5. Hebert, L.E., et al., *Annual incidence of Alzheimer disease in the United States projected to the years 2000 through 2050*. Alzheimer Dis Assoc Disord, 2001. **15**(4): p. 169-73.
6. Iadecola, C., et al., *SOD1 rescues cerebral endothelial dysfunction in mice overexpressing amyloid precursor protein*. Nat Neurosci, 1999. **2**(2): p. 157-61.

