High blood pressure (BP) in midlife is predictive of Alzheimer's disease (AD) in later life. Similarly, reductions in BP are associated with protection against AD [1, 2] such that even small reductions (<5mmHg systolic and <3 mmHg diastolic) are associated with improvements in Mini Mental State Examination (MMSE) [1] scores. Specifically, converging evidence indicates that lowering BP alters the pathobiological factors that contribute to AD (see Birns et al. review [2]). Treatment with antihypertensive medications, specifically angiotensin converting enzyme inhibitors (ACE-I) such as ramipril, is associated with up to a 55% reduction in the prevalence of AD, suggesting a potentially promising role for ACE-I in the prevention of AD [3]. ACE-I improve endothelial function outside of the central nervous system and decrease A β (i.e. a substance thought to contribute to neuronal damage in AD) in animal models, suggesting that these are mechanisms by which ACE-Is may protect against AD [4]. It is unknown however 1) whether ACE-Is will have the same effect on cerebrospinal fluid (CSF) A β levels in humans as in animal models 2) whether ACE-Is induce changes associated with vascular function (i.e. levels of CSF angiotensin converting enzyme (ACE) and peripheral endothelial function) and 3) whether there are interactions between ACE-I-induced changes in CSF A β , CSF ACE and indices of vascular function.

In order to better understand the mechanisms through which ACE-I may modify CSF A β and possibly AD risk, we propose a randomized, double-blind, placebo-controlled pilot clinical trial, enrolling 20 middle-aged (age range 40 –70 years), mildly hypertensive (130 – 160 mmHg mean systolic and 70 – 100 mmHg mean diastolic) participants, who are adult children of an individual with AD. The main objective of this trial is to examine the effects of the ACE-I, ramipril, on 1) CSF A β levels 2) CSF ACE levels and 3) peripheral endothelial function as measured by brachial artery flow-mediated vasodilation (FMD) and aortic augmentation index (AAIx), in middle-aged adults with mildly elevated BP, who are at increased risk of developing AD based on familial history.

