B. 3. ACE-I Improve Cognition in Humans with AD by Decreasing A β Levels: One mechanism by which antihypertensives may protect against AD is via A β neuropathology [4, 24]. Some of the most promising clinical [3, 26] observational [29] and basic science [24, 27] data examining the effects of antihypertensives on AD comes from studies using ACE-I. Angiotensin converting enzyme (ACE), a component of the renin–angiotensin system (RAS), has been shown to facilitate in the accumulation of A β plaques [30, 31], while ACE-I are reported to reduce A β deposition [32]. The chief rationale for using ACE-I is based on findings that ACE receptors are over-expressed in the hippocampus and throughout blood brain barrier (BBB) cells in patients with AD [30 {Savaskan, 2005 #5900, 33}. Furthermore, many ACE-Is such as the one in the current proposal, have the ability to cross the BBB, a factor that may contribute to ACE-I selective ability to treat AD via prevention of A β deposition. In fact, studies have demonstrated that treatment with centrally acting ACE-I decreases A β in animal models of AD [32], decreases AD incidence [34] and improves cognitive performance in AD patients [35]. These preclinical studies suggest that centrally acting ACE-Is may have AD-modifying activity in participants with AD or in those at high risk of developing AD.

Targeting modifiable risk factors, such as elevated BP, that contribute to A β accumulation and subsequent AD pathology may be important in developing effective preventive strategies for AD. The mechanisms through which adjustable risk factors contribute to neuronal damage may potentially be modified. ACE is associated with elevated BP and the accumulation of A β plaques [16, 19-22]. If the presence of A β leads to neuronal damage in part through deregulation of ACE levels and elevated blood pressure, then modifying A β accumulation through the use of ACE-Is may potentially reduce the risk of developing AD in high-risk individuals.

B. 4. Significance: The proposed 4-month randomized, double-blind, placebo-controlled, pilot clinical trial will provide information concerning possible mechanisms underlying the potential efficacy of ACE-I to reduce the risk for AD. If ramipril improves CSF A β levels and these changes correlate significantly with changes in CSF ACE levels, peripheral measures of endothelial function and/or cognition in persons at risk for AD, it would strengthen the evidence

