for the role of ACE-I in AD prevention. Preventing or delaying the onset of AD would have a profound population health and economic impact on the people of Wisconsin and worldwide.

B. 5. Importance of Prevention: Recent estimates of the projected rapid increase in the prevalence of AD emphasize the importance of early detection, intervention, and prevention of the disease.[36] There is increasing evidence that the clinical syndrome of AD is preceded by a prolonged and currently irreversible preclinical phase characterized by neuropathological, [37] functional, [38, 39] structural, [40] metabolic, [39, 41] and cognitive changes[42-45] typical of AD. There is growing evidence that a person's risk of developing AD may be influenced by lifestyle, [46-52] diet, [53-55] vascular risk factors, [9, 10, 12, 14, 17, 56, 57] use of vitamin supplements, [58-60] and use of nonsteroidal anti-inflammatory agents [61-63]. However, there are currently no known effective interventions targeting these potentially modifiable factors to either prevent the development of MCI, postpone the conversion of MCI to AD, [64, 65] or slow the progression of established disease [66]. The increasing prevalence of AD, lack of effective treatments, and increasing identification of potentially modifiable risk factors emphasize the critical need for systematic research targeting preclinical diagnosis and identification of early intervention and prevention strategies.

B. 6. Modifiable and Non-modifiable Risk Factors for AD.

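### Does the correlation between changes in B.4 need a stated arm term, given that pooling the two arms could produce it without any within-arm link?

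*Combined protocol and SAP*

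**What the plan says.** The protocol speaks of relating one change to another in three places.

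- A.1 (Rationale) lists as its third unknown "whether there are interactions between ACE-I-induced changes in CSF A β , CSF ACE and indices of vascular function".
- B.4 (Significance) sets out a two-part condition. Ramipril must improve CSF Aβ, and "these changes correlate significantly with changes in CSF ACE levels, peripheral measures of endothelial function and/or cognition in persons at risk for AD". Meeting both would add to the evidence "for the role of ACE-I in AD prevention".
- D.4 (Data Analysis) has one sentence that could cover such an analysis: "Regression models will be used to evaluate predictors of change in CSF variables and endothelial outcomes". It names no predictors, no arm term and no analysis set.

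The treatment comparison is described separately in D.4, as "repeated-measures analysis of variance (ANOVA) to assess the effects of ramipril vs. placebo, using covariates as applicable (ANCOVA"), two-sided at 0.05. Specific Aims 1 to 3, the endpoints in D.1.3 and the objective that opens D.4 are all ramipril-versus-placebo comparisons. The 2014 update in section C reports that results are published, but D.4 also says that "additional analyses on data from this trial need to be conducted".

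**The concern.** The hypothesis in A.2 is that ramipril moves Aβ, ACE and endothelial function together. If so, a scatter plot of one change against another, with all 20 participants on it, shows two clouds displaced along both axes. A correlation that ignores arm then differs from zero even if, within each arm, one change says nothing about the other. The second half of the B.4 condition would follow largely from the arm differences themselves and would add little independent support. A reader could take it as a mechanistic link when it shows only that both variables responded to the drug. B.4 does say that the trial will inform possible mechanisms, and work on the data continues, so the question is a reasonable one to raise.

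**Working it through.** **Inputs from the protocol.** Ten participants per arm (D.1.3); two-sided 0.05 (D.4); the power statement in D.4, "A sample size of 10 subjects per arm should have greater than 80% power to detect an 8% change in CSF" Aβ, and more than 90% for the endothelial variables. No SD is given for any outcome, and no power figure for ACE or cognition.

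**The plan's own figure.** Without an SD or a named test, the power statement cannot be reproduced. It can only be inverted for the standardized effect d it would imply.

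- Two-sample t-test, 18 df, noncentrality d·√(10/2): 80% power needs d = 1.325 and 90% needs d = 1.534.
- Paired t-test within one arm of 10, 9 df, noncentrality d·√10: 80% needs d = 0.996 and 90% needs d = 1.155.

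**Correlation created by pooling.** Let both changes have unit variance and zero correlation within arms, with the ramipril arm shifted by d1 and d2. With equal arms, pooling adds d1·d2/4 to the covariance and d²/4 to each variance, so

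r = (d1·d2/4) / √[(1 + d1²/4)(1 + d2²/4)].

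- d1 = d2 = 0.5: 0.0625/1.0625 = 0.06
- d1 = d2 = 1.0: 0.25/1.25 = 0.20
- d1 = d2 = 1.325: 0.439/1.439 = 0.31
- d1 = d2 = 1.5: 0.5625/1.5625 = 0.36

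The critical |r| for n = 20 (18 df) is 0.444.

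**How often it reaches p<0.05.** Simulation with 400,000 trials per row, normal data, no within-arm link. The last column keeps only trials with a significant Aβ arm difference, since B.4 requires an Aβ improvement first.

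| Shift in Aβ / other variable (SD) | Pooled, no arm | Pooled, given significant Aβ effect |
|---|---|---|
| 0.5 / 0.5 | 5.7% | 8.3% |
| 0.8 / 0.8 | 9.0% | 13.6% |
| 0.996 / 0.996 | 13.7% | 19.0% |
| 1.0 / 1.0 | 13.8% | 19.0% |
| 0.996 / 1.155 | 16.1% | 22.9% |
| 1.325 / 1.0 | 19.0% | 21.8% |
| 1.325 / 1.325 | 27.4% | 32.0% |
| 1.325 / 1.534 | 32.8% | 38.5% |
| 1.5 / 1.5 | 37.6% | 41.0% |
| 1.325 / 0 | 4.9% | 4.9% |

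With arm in the model (17 df), and with the ramipril arm alone (8 df), the rate is 4.9% to 5.1% in every row.

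**What each choice can detect.** For 80% power, |r| = tanh(2.80/√(n − k − 3)) with k covariates.

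- Pooled, n = 20, k = 0: tanh(2.80/√17) = 0.59
- With arm, n = 20, k = 1: tanh(2.80/√16) = 0.60
- Ramipril arm only, n = 10, k = 0: tanh(2.80/√7) = 0.79

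**Which of these does the text call for?** A.1 asks about changes that the ACE inhibitor induces. B.4 refers back to the changes that follow when ramipril improves Aβ. Both describe change under ramipril, which suits a ramipril-arm or arm-adjusted analysis at least as well as a pooled one. The D.4 sentence concerns predictors of change, and in a randomized trial treatment arm is the first predictor anyone would enter. No sentence says that the arms are pooled without it.

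**The case for a change.** The strongest case for acting is that the effect is real under the trial's own hypothesis, that it grows once the Aβ condition in B.4 is imposed, and that prevention costs almost nothing. Treatment assignment is among the data that D.4 lists for transfer. An arm term uses one degree of freedom and moves the detectable |r| only from 0.59 to 0.60. Further analyses are announced, and the update in section C mentions pending grant applications that build on this research, so a misread correlation could travel.

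The arithmetic in that case stands, and so does the observation that the analysis is not specified. It does not show that anything in the plan is wrong. The inflated rates belong to one of three possible analyses, and the protocol does not choose that one. The upper figures also lean on effects back-solved from a power statement that names no test. If that statement meant change within an arm, the shifts would be 0.996 and 1.155 SD and the rates 14% to 16%. For ACE and cognition there is no power figure to solve from.

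Nor is the pooled result a false positive in the usual sense. The marginal correlation truly differs from zero, and the fault would lie in how it is read. B.4 concludes only that the evidence for a role in prevention is strengthened, which is broader than a claim of mediation.

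Finally, the remedy is open to fair disagreement. A common slope adjusted for arm draws on placebo participants, who have no drug-induced change, and assumes equal slopes in the two arms. A ramipril-only correlation fits A.1 more closely, but detects only |r| of about 0.79 with 80% power.

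**Conclusion.** No change to the plan is needed. The text leaves out the arm term and analysis set for a supportive correlation mentioned in background sections, and an analyst of a randomized trial would ordinarily supply both. The consequence would be material only if three things held together: the arms were pooled, arm was left out, and ramipril shifted both variables substantially. Then the correlation would reach significance without a within-arm link in about 6% (0.5 SD), 14% (1.0 SD), 27% (1.325 SD) or 38% (1.5 SD) of trials when both shifts are equal, against about 5% otherwise. These figures assume normal data, all 20 participants completing and zero within-arm correlation. The shifts are assumptions, since the protocol gives no SD. Specific Aims 1 to 3 and the listed endpoints rest on arm comparisons and are unaffected. Anyone reporting such a correlation in the remaining work would do well to say which participants and terms it used and to call it exploratory. That is good reporting practice and does not correct a defect in the plan.
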